We will collect electromyography (EMG), joint angle, and footswitch data at 1000 Hz using a 24-channel hard-wired analog to digital board and a custom written Labview software acquisition program (National Instruments, Austin, TX) during stepping using BWST or overground and manual assistance. EMG data will be sampled from 0.1 to 1 kHz and AC coupled into a differential amplifier (Konigsberg Instruments, Pasadena, CA). Following standard skin preparation, bipolar surface EMG electrodes with a fixed distance between the electrodes will be placed on the soleus, medial gastrocnemius, tibialis anterior, medial hamstrings, adductor, vastus lateralis, and rectus femoris bilaterally. Limb kinematics will be digitally acquired a passive marker high speed motion capture system (Motion Analysis, Santa Rosa, CA). Individual limb loads will be measured with shoe-insole pressure sensors (FSCAN, Tekscan, Boston). Data will be processed and synchronized using Labview software (National Instruments, Austin, TX) customized by our laboratory. EMG data will be full wave rectified and filtered using a 4th order bandpass Butterworth filter (40 Hz - 500 Hz). Mean EMG represents the relative number and frequencies of the motor units recruited per burst. Integrated EMG assesses the total EMG activity generated per step. EMG mean and integrated amplitudes from each muscle will be compared before and after locomotor training. Co-activation values of flexors and extensors will be calculated. The degree of coordination in the stepping-related oscillations of lower limb segments will be assessed through principal component analysis. Quantitative measurements and statistical testing have been described in detail in previous publications listed above.

Heart rate will be monitored using a digit pulse oximeter placed on the index finger of the research participant during training sessions and experiments.

Next analytical approaches will be utilized in these studies:

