- **EMG burst cycle analysis.** EMG signals will be band pass filtered between 40-500 Hz to eliminate any transient signals and then rectified. A minimum threshold for EMG activity (3 standard deviations (SD) above mean baseline noise) will be selected for each channel. Onset of EMG bursts is detected as the location where the signal amplitude remains above the threshold for 50 continuous samples, and the end as the location where the signal amplitude remains below the threshold level for 150 continuous samples. Detected start and end points are displayed as marks on the data for verification. Mean EMG (MEMG) may be used to make interpretations about the relative number and firing frequencies of the motor units recruited per burst. Integrated EMG (IEMG) assesses the total EMG activity generated per step.
- **Muscle co-activity and clonicity.** We developed a method to quantify the clonicity of and coactivation among muscles during human locomotion based on a Bayesian approach to EMG analyses, using reversible jump Markov chain Monte Carlo (RJMCMC) simulation ([name] et al. 1997). In Bayesian analyses, data are passed through a simulation algorithm multiple times (300,000), generating distributions of the quantities of interest. The Bayesian process yields an objective assessment of the mean and deviation of parameters of a signal (in this case co-activity and clonicity), thereby, minimizing research participative error. Further, the measures vary less than 0.5% after repeating the measures three times across five data sets. This approach allows for statistically valid inferences about these quantities and the differences between them.
- **Linear envelopes.** The high-pass filtered and rectified EMG data will be low-pass filtered at 5 Hz. EMG bursts may be averaged relative to the start of a burst in the muscle, the start of a burst in another muscle, or to a biomechanical event such as the rise or decline of force. Averages will be generated from data normalized to the duration of each burst or step cycle. Averaged waveforms are of interest because they may be assumed to represent the typical activity pattern. Coefficients of variation will be calculated to scale standard deviations to a mean value throughout the step cycle.

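### Section G names rectification before the 40-500 Hz filter in one place and after it in another, for the same mean and integrated EMG; the first order, taken literally, would empty both measures (minor correction)

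*Protocol*

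**What the plan says.** Three places in section G of the protocol describe the EMG signal chain.

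- **Locomotor Training Intervention, data-collection paragraph:** "EMG data will be full wave rectified and filtered using a 4th order bandpass Butterworth filter (40 Hz - 500 Hz". The next sentences define the two amplitude measures on this signal: "Mean EMG represents the relative number and frequencies of the motor units recruited per burst", and "Integrated EMG assesses the total EMG activity generated per step". The paragraph then commits to using them: "EMG mean and integrated amplitudes from each muscle will be compared before and after locomotor training".
- **EMG burst cycle analysis bullet:** "EMG signals will be band pass filtered between 40-500 Hz to eliminate any transient signals and then rectified". This bullet sets the burst threshold and the onset rule, and then defines mean EMG and integrated EMG again in nearly the same terms.
- **Linear envelopes bullet:** "The high-pass filtered and rectified EMG data will be low-pass filtered at 5 Hz". Filtering is again named before rectification.

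The sampling rate is given once: "We will collect electromyography (EMG), joint angle, and footswitch data at 1000 Hz".

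**The concern.** Rectification is nonlinear. It turns a signal that swings around zero into one whose local average follows the strength of the contraction, so after rectification the amplitude information sits at zero and low frequencies. A band-pass with a 40 Hz lower edge blocks those frequencies. Filtering first and rectifying second is safe, because the filter then acts on the raw oscillation and the rectifier creates the amplitude signal afterwards. In the reverse order, the filter deletes what the rectifier has just created.

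The sentence that names rectification first stands directly before the definitions of mean and integrated EMG and the plan to compare them before and after training. An analyst who followed it literally would obtain values near zero at both times, whatever the muscles did. Absence of change would then be a product of the processing and not a finding about the participants.

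**Working it through.** The protocol states no figure on this point, so there is none to reproduce. The check takes the written steps and asks what each order does to the two measures.

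**Inputs from the protocol.** Band 40-500 Hz, 4th order Butterworth; sampling at 1000 Hz; threshold 3 SD above mean baseline noise; onset after 50 continuous samples above threshold; mean EMG per burst; integrated EMG per step.

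**Assumptions, not in the protocol.** Gaussian EMG shaped to 20-350 Hz; bursts of 0.5 s in a 1.2 s step; 30 steps; burst SD 1 or 2; baseline SD 0.05. At 1000 Hz sampling a 500 Hz upper edge equals half the sampling rate and cannot be entered in a digital band-pass design. Upper edges of 499 Hz and 450 Hz, and a plain 40 Hz high-pass, stood in for it. The design order (2 or 4) and causal or zero-phase filtering were also varied.

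**Step 1, without simulation.** Let x be the raw signal, r = |x|, and H the filter's gain. Over whole steps the sum of the filtered signal is H(0) × (sum of r). A filter with a 40 Hz lower edge has H(0) = 0, so the integral is 0 for any r. Doubling the amplitude doubles r and still gives 2 × 0 = 0. The step rhythm itself is also lost. Its frequency is 1/1.2 = 0.83 Hz, and well below the edge the gain is about (f/40)^n. That is (0.83/40)^2 ≈ 0.0004 for order 2 and (0.83/40)^4 ≈ 0.0000002 for order 4.

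**Step 2, what the measures should be.** For a Gaussian signal the mean of |x| is SD × √(2/π) = 0.798 × SD, so 0.80 at SD 1 and 1.60 at SD 2. The simulated plain rectified signal gave 0.79 and 1.59, as expected.

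**Step 3, the two orders by simulation (ranges over the filter variants).**

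| Measure | Filter, then rectify | Rectify, then filter |
|---|---|---|
| Mean EMG per burst, burst SD 1 | 0.75 to 0.77 | within -0.0005 to 0.009 |
| Mean EMG per burst, burst SD 2 | 1.50 to 1.54 | within -0.0005 to 0.009 |
| Integrated EMG per step, burst SD 1 | 0.40 to 0.41 | about -0.000002 to -0.000005 |
| Integrated EMG per step, burst SD 2 | 0.78 to 0.80 | about -0.000002 to -0.000005 |
| Longest run above threshold (samples) | 55 to 157 | 7 to 14 |

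The largest ratio for mean EMG is 0.0086 / 1.505 = 0.0057, or about 0.6%. With filtering first, doubling the burst SD doubles mean EMG (0.77 to 1.54). With rectification first, integrated EMG stays at zero. About 48% to 57% of in-burst samples are then negative, which a rectified amplitude signal cannot be.

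**Step 4, the onset rule.** The rule reads "Onset of EMG bursts is detected as the location where the signal amplitude remains above the threshold for 50 continuous samples". With rectification first the longest run is 14 samples, below the required 50, so no burst would be detected.

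**The case against.** The strongest reply is that the sentence does not state a sequence. It joins the two steps with *and*; only the burst cycle bullet says *and then*. The sentence may simply list the operations, with the same 40-500 Hz band, and leave the order to the analytical bullets that follow. Those bullets define the same two measures under an explicit filter-first order and name filtering first again for the linear envelopes. A working chain is therefore already in the plan. The error would also be hard to miss: no bursts would be detected, half the samples would be negative, and detected burst limits are plotted for checking. All of this stands, and it limits the weight of the point. It does not remove it: nothing says which sentence governs, and the one with the unsafe word order sits next to the planned comparison.

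A reader might infer more than the document supports, in four ways.

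- *That the trial's EMG results are void.* This would need the team to follow one sentence literally and ignore the bullets. Nothing shows that any recording was processed that way.
- *That mixed processing could create a spurious change of about 40%.* Rectifying a second time after the filter would give mean EMG about 40-45% below the filter-first value (0.41-0.46 against 0.75-0.77 at burst SD 1). No section states a second rectification, and nothing suggests different chains for different recordings.
- *That selection for surgery is biased.* Section D repeats the experiments after 80 training sessions, before surgical eligibility is discussed, but it does not say that mean or integrated EMG decides eligibility.
- *That co-activation must use the same chain.* The co-activity and clonicity bullet has its own Bayesian method and does not state its input signal.

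**Conclusion.** The sentence is wrong as written and conflicts with the burst cycle bullet on the same two measures. Followed in its word order, it would reduce mean EMG per burst to no more than about 0.6% of the filter-first value and integrated EMG per step to about zero, and the pre/post comparison of these amplitudes would be empty. The zero for the integral follows from the filter alone. The 0.6% rests on the assumed burst length, step length and signal shape, and it held across every filter variant tried.

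The point is minor. The safe order already appears in the plan. Sections A and G judge success by standing and stepping performance against the best results of earlier patients who were only trained, not by EMG amplitude. Section j plans no statistical comparison. That does not excuse the sentence, since descriptive pre/post values would be just as empty, but a claim that the trial's conclusions are at risk would go beyond the document.

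**What to change.** In section G, Locomotor Training Intervention, reword the sentence to: *EMG data will be band-pass filtered (4th order Butterworth, 40-500 Hz) and then full wave rectified*, in line with the EMG burst cycle analysis bullet. Add that mean EMG, integrated EMG and burst detection all use this order.

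Confirm the order in the laboratory's processing software. Reprocess stored recordings only if that check shows that rectification came first.

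The cost is one or two sentences and one software check. No new data are needed, and no procedure for participants changes.

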- **Scatter plots.** Scatter plots will be used to detect relationships among muscle EMG, limb loading, stepping velocity, and joint position. Scatter plots will be generated from individual steps and averaged waveforms. EMG amplitudes (5 Hz low pass filtered) of agonist and antagonist muscles will be plotted (triceps surae (TS), tibialis anterior (TA), hamstring (HM), quadriceps (Q), and adductor (ADD) to assess muscle coordination. This provides information about the phasing of a muscle activity relative to other muscles. The relationship between EMG activity and either phases of loading or joint position will also be plotted. Three-dimensional relationships incorporating two of the latter variables and muscle EMG will also be utilized.
- **Voluntary response index.** Voluntary motor task EMG from healthy individuals has been averaged across a five second window to generate response vectors (RVs). The prototype response vector (PRV) was generated by normalizing the RVs by the vector magnitude and then averaged. The PRV is comprised of 10 elements, one for each

muscle. A PRV is created for each phase of each movement in the voluntary motor task component of the BMCA protocol. A similarity index (SI) is then used for comparison of the data. The SI is a numerical expression of the similarity of the distribution of the EMG activity in the RV, computed as the normalized dot product between the two vectors (vector representing the distribution of activity generated by healthy research participants, and that representing the distribution of activity in the test research participant). A value of 1.0 for the SI represents an identical distribution.

- Kinematic and kinetic analysis. Joint kinematics will be analyzed using EVaRT and Orthotrak which provide instantaneous 3-D graphic displays and all kinematic parameters of the motion performed by a research participant. The force signals will be acquired from FSCAN at 50 Hz and interpolated to 1000 Hz and low-pass filtered (5 Hz). A minimum threshold (3 SD above baseline) will be calculated for each signal. BWS was acquired by Labview A/D and processed by customized software.

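### As written, the EMG burst-onset rule runs on unsmoothed rectified EMG, so it misses small and moderate bursts and marks the others late by an amount that depends on amplitude (minor)

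*Protocol*

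**What the plan says.** The *EMG burst cycle analysis* bullet in section G of the Protocol sets out a complete ordered rule:

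- Pre-processing: "EMG signals will be band pass filtered between 40-500 Hz to eliminate any transient signals and then rectified".
- Threshold: "A minimum threshold for EMG activity (3 standard deviations (SD) above mean baseline noise) will be selected for each channel".
- Onset: "Onset of EMG bursts is detected as the location where the signal amplitude remains above the threshold for 50 continuous samples".
- End: "the end as the location where the signal amplitude remains below the threshold level for 150 continuous samples".
- Check: "Detected start and end points are displayed as marks on the data for verification".

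The only EMG low-pass filter in the document belongs to two other analyses. Under *Linear envelopes*: "The high-pass filtered and rectified EMG data will be low-pass filtered at 5 Hz". Under *Scatter plots*: "EMG amplitudes (5 Hz low pass filtered) of agonist and antagonist muscles will be plotted". The onset rule refers to neither.

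The acquisition paragraph under *Locomotor Training Intervention* gives a sampling rate of 1000 Hz. It names rectification first and the 40-500 Hz fourth-order Butterworth filter second, the reverse of the order in the burst bullet. It also describes mean EMG as a per-burst quantity and integrated EMG as a per-step quantity, and plans to compare both before and after training.

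**The concern.** A run-length rule of this kind suits a smooth envelope. Rectified EMG without smoothing is not an envelope: it returns towards zero at every zero crossing of the underlying signal. Asking it to stay above a positive threshold for 50 ms without a break is a demand on amplitude rather than on whether the muscle is active. Both the chance of detecting a burst and the time at which it is marked then depend on its size.

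What is at stake is limited but real. Mean EMG is read over detected bursts. The *Linear envelopes* analysis may align averages to burst start, and "Averages will be generated from data normalized to the duration of each burst or step cycle". If amplitude rises with training or with stimulation, a detector of this kind can make an amplitude change look like a timing change, or can compare different subsets of bursts in the two conditions.

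**Working it through.** The Protocol states no detection rate or timing error, so there is no planned figure to reproduce. The check applies the stated rule to simulated signals.

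**Inputs from the Protocol.** Sampling at 1000 Hz, so 50 samples = 50 ms and 150 samples = 150 ms; lower band edge 40 Hz; threshold = baseline mean + 3 SD; onset run 50, end run 150.

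**Assumptions not in the Protocol.** Gaussian EMG; three spectra (white, 40-200 Hz, 30-150 Hz); burst lengths 300, 500 and 1000 ms; abrupt (rectangular) or gradual (Hann) shape; k = burst RMS / baseline noise SD from 3 to 100. The upper band edge was set at 499 Hz, because 500 Hz is the Nyquist limit at 1000 Hz.

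**Step 1, zero crossings.** A signal with no content below 40 Hz crosses zero at least about 2 × 40 × 0.050 = 4 times in 50 ms. Once rectified, it touches zero at each crossing.

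**Step 2, threshold.** Rectified Gaussian noise of unit SD has mean 0.798 and SD 0.603, so the threshold is 0.798 + 3 × 0.603 = 2.61.

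**Step 3, analytic check with independent samples.** The share of burst samples above threshold is p = 2[1 − Φ(2.61/√(k²+1))].

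- k = 5: p = 0.609, p^50 = 1.7 × 10⁻¹¹
- k = 10: p = 0.795, p^50 = 1.1 × 10⁻⁵
- k = 20: p = 0.896, p^50 = 0.0042
- k = 50: p = 0.958, p^50 = 0.12

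A 500 ms burst has 451 possible run starts. The expected number of qualifying runs is about p^50 × [1 + 450(1 − p)]. At k = 20 this is 0.0042 × (1 + 450 × 0.104) ≈ 0.20, so the chance of at least one is about 1 − e^(−0.20) = 18%. Direct simulation of unfiltered independent samples gave 17%.

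**Step 4, simulation of the rule as written** (band-pass, rectify, threshold on the rectified baseline; 200 bursts per cell; ranges over spectra and shapes). Percentage of bursts detected:

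| k | 300 ms | 500 ms | 1000 ms |
|---|---|---|---|
| 3, 5 | 0 | 0 | 0 |
| 10 | 0-2 | 0-4 | 0-4 |
| 15 | 2-10 | 4-16 | 6-32 |
| 20 | 10-28 | 18-34 | 39-64 |
| 30 | 43-55 | 62-72 | 87-94 |
| 50 | 79-86 | 94-96 | 100 |
| 100 | 96-100 | 100 | 100 |

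The values above half at k = 20 are the 1000 ms Hann bursts (56-64%); 1000 ms abrupt bursts gave 39-43%.

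**Step 5, onset delay.** For detected 500 ms abrupt bursts the median delay was 187-244 ms at k = 20, 147-196 ms at 30, 60-91 ms at 50 and 18-24 ms at 100.

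**Step 6, the other order.** Rectifying first and then removing content below 40 Hz gives a signal that swings about zero. A 40 Hz half-cycle lasts 12.5 ms, so a 50 ms run above a positive threshold is not to be expected. Simulation found 0% at k = 5 to 100.

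**Step 7, effect on Mean EMG** (600 ms bursts, marks used unverified). When amplitude doubles from k = 20 to 40 and burst amplitude varies with log SD 0.3-0.5, the rule reads a ratio of 1.43-1.84; the true ratio in the simulated data was 1.89-2.05. With no burst-to-burst variation it reads 1.96-2.12, which is nearly unbiased.

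**Step 8, with an envelope.** With the same 3 SD and 50-sample rule, a 20 Hz zero-phase low-pass found 100% of 500 ms abrupt bursts at k = 2 to 50. A 10 Hz second-order envelope found 499-500 of 500 bursts at k = 2 to 100.

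**The case against.** The best defence is that the bullet is a summary. The acquisition paragraph refers to earlier publications for detail and to LabVIEW software customised by the laboratory, and the amplitude in the rule may have been meant as an envelope. The rule's failure would also be obvious: an operator checking the displayed marks would see almost none on small bursts. Both arguments stand as reasons to expect little practical harm. They do not repair the text, because the Protocol fixes the numerical steps itself, names a low-pass where it wants one, and puts none before this threshold.

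The assumptions are a fair second objection. The Protocol gives no burst-to-noise ratio, length or shape, and with long gradual bursts more than half are found at 20 times noise, so there the loss of most bursts stops near 15 times.

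Three stronger readings are tempting and are not supported:

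- *That the rule fails specifically under stimulation because responses are locked to the pulses.* Stage 1C describes the stimulation as subthreshold, tonic and non-patterned, and no passage gives the waveform of the EMG under it. Nor is there a basis in the documents for ruling out a 20 Hz cut-off on that ground.
- *That burst ends are late and neighbouring bursts merge as a matter of course.* This depends on the baseline SD. On rectified noise (threshold 2.61) about 150 × 0.0091 = 1.4 noise samples exceed the threshold in each 150-sample window. On unrectified noise (threshold 3.00) it is 150 × 0.0027 = 0.41, and the effect nearly disappears. The text does not say which is meant.
- *That the trial's main conclusion is at risk.* Success is judged on stepping and standing performance against the best earlier results with training alone, which does not use this detector.

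**Conclusion.** The point holds for the rule as written and is minor. Applied literally, the rule finds almost no bursts up to about 10 times baseline noise and misses most up to about 15-20 times, depending on assumed burst length and shape. It marks the detected ones late, by an amount that shrinks as amplitude rises. In the order given in the acquisition paragraph it finds none.

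The reach is confined to descriptive per-burst measures: Mean EMG before versus after training, and averages aligned to burst start or normalised to burst duration. Integrated EMG is per step and is untouched, as are averages aligned to biomechanical events or to the step cycle. Section j plans no statistical comparison, so no error rate or sample size is involved.

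The qualitative result follows from the 40 Hz band edge and the 50 ms run. The percentages and delays rest on the simulated signals. Whether the laboratory's software smooths first cannot be seen from the Protocol.

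**What to change.** In the *EMG burst cycle analysis* bullet, apply the threshold and both run-length rules to a zero-phase low-pass envelope of the band-passed, rectified EMG. State the cut-off (for example 10-20 Hz) and the filter order. Compute the baseline mean and SD on that same envelope, which also settles the ambiguity in the end rule. Use one setting before and after training and with and without stimulation. Reconcile the filter and rectification order between this bullet and the acquisition paragraph. If the software already smooths, one sentence saying so and giving the setting is enough.

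The cost is wording and a software setting; recorded signals can be reprocessed. The trade-off is timing blur. For abrupt bursts in simulation, onsets fall 10-38 ms early at 10 Hz (ends 10-39 ms late) and 4-19 ms early at 20 Hz. Some amplitude dependence remains for gradual bursts: at 10 Hz with half-sine bursts, onset is 55-61 ms late at 2 times noise, 5-7 ms late at 10 times, and 4-16 ms early at 20-100 times. Re-using the plan's own 5 Hz filter would blur more, with onsets about 35-69 ms early for 500 ms abrupt bursts.

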We propose that daily locomotor training in the presence of SCES will enable the individual with clinically complete SCI to stand and step independently while bearing full weight. Non-patterned electrical stimulation of the lumbar spinal cord can induce patterned, locomotor-like activity in individuals with clinically complete SCI [1]. Modifying the frequency of stimulation can induce extensor patterns similar to that observed during standing [45]. In addition, when afferent information is also provided there is further modulation of these motor patterns elicited by epidural stimulation [46]. Individuals with a clinically complete spinal cord injury can execute independent steps using a body weight support system on a treadmill (BWST) using manual assistance without epidural stimulation. When combined with SCES, we anticipate the training will be even more successful, enabling prolonged periods of independent stepping and standing. Although there will not be a separate control group studied simultaneously, historical controls will consist of the best stepping and standing performance that have been observed previously in our laboratory in individuals that have a clinically complete SCI. Performance beyond this threshold by any individual treated with both epidural stimulation and training will be interpreted as a significantly better intervention than training alone.

Future studies will eventually focus on development and implementation of the more advanced multi-electrode array technique that will provide functionally-adaptive site-specific stimulation. The adaptive stimulation strategy proposed here takes advantage of capabilities of our new array design that are not possible using either conventional or commercially available electrode arrays. Our future arrays will provide two key benefits:

- Our electrode arrays cover a larger area than commercially available arrays, extending from the midthoracic to the sacral extents of the spinal cord. It is possible that the optimal stimulation sites for facilitating stepping versus standing may be spatially distinct on the spinal cord. If this is the case, conventional arrays are less likely to be able to recover both stepping and standing in the same patient.

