These results will reveal whether conventional electrodes can be used to facilitate stepping in clinically complete spinal cord injury patients. This study will clarify whether the optimal spinal cord sites for using epidural stimulation to induce stepping and standing migrate over the course of training in the human spinal cord. We expect that these data will provide further evidence of the plasticity of the injured spinal cord, and that training modifies the spinal networks for stepping. Stepping performance of the patients will be compared against historical controls that were given step training without epidural stimulation. The criteria for success of the combined treatment will be determined by the best outcomes that have been obtained for previous patients who were only trained.

h. Treatment regimen(s) (*for medically invasive research*)

i. Clinical information (when applicable) (*for medically invasive research*)

j. Statistical analysis of the collected data

No statistical analysis will be used for comparison of data. This study is designed as a proof of principle study without statistical power to demonstrate the feasibility of the methods.

k. Data and Safety Monitoring Plan

Entity responsible for monitoring is identified:

The study will be monitored by a Data Safety Monitoring Board consisting of: [name] (Neurosurgeon), [name] (physiatrist); [name]

[name] (cardiologist) and [name] (Urologist) who are not associated with the study.

Policies and procedures for adverse event reporting are described:

If a subject develops an adverse event it will be reported to the DSMB, local IRB and Sponsor within 24 – 48 hours of being notified of the event.

Protocol Compliance:

Any deviations in the protocol will be documented and reported to the IRB.

Plans for measuring appropriate intervals between safety reviews and predetermined criteria for stopping the study:

Research participants will be continuously monitored for complications, adverse events and/or serious adverse events. If any complications arise during the course of the study the local Medical Advisor ([name]) will be notified. All study procedures will be halted until the complication, adverse event and/or serious adverse event has been reviewed by the medical advisor and it has been determined that it is safe for the study participant to return to participating in study procedures.

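### The protocol promises significance, statistical testing and valid inference on differences, section j rules out any statistical comparison, and the support offered for the EMG inference omits session-to-session variation

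*Protocol*

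**What the plan says.** Four places in the protocol bear on whether differences will be judged statistically.

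- **Section A (Background).** There is no concurrent control group. Performance by any individual beyond the best seen earlier in the laboratory with training alone "will be interpreted as a significantly better intervention than training alone".
- **Section G, Locomotor Training Intervention, paragraph on EMG collection.** Mean and integrated EMG amplitudes are to be compared before and after training, and co-activation values are to be calculated. The paragraph closes: "Quantitative measurements and statistical testing have been described in detail in previous publications listed above".
- **Section G, item on muscle co-activity and clonicity.** In the Bayesian analysis, "data are passed through a simulation algorithm multiple times (300,000), generating distributions of the quantities of interest". The output is described as the "mean and deviation of parameters of a signal (in this case co-activity and clonicity"). The item adds that "the measures vary less than 0.5% after repeating the measures three times across five data sets" and concludes: "This approach allows for statistically valid inferences about these quantities and the differences between them".
- **Section j.** "No statistical analysis will be used for comparison of data". It continues: "This study is designed as a proof of principle study without statistical power to demonstrate the feasibility of the methods".

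**The concern.** There are two linked problems.

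The first is a contradiction. Section j does not defer the comparison of data to another document; it excludes it. Sections A and G nevertheless speak of significance, of testing and of valid inference on differences. A reader cannot tell whether a later statement that co-activity or clonicity changed, or that stimulation was significantly better, lies inside the plan or outside it.

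The second is the evidence offered for validity. A posterior for the parameters of a signal describes uncertainty given that signal. Repeatability of a measure describes how stable the measuring is. Change between two sessions also contains whatever differs between the sessions: electrode placement, level of body weight support, manual assistance, the participant's state that day. The protocol itself says that body weight support is reduced over training and that trainers help only as needed, so sessions will differ. It gives no session-to-session SD.

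This matters because section B proposes that training acts partly by reducing clonus and restoring reciprocal inhibition, and clonicity and co-activation are the listed measures closest to those mechanisms. Section D says that the repeat after the 80 screening sessions is meant to show that training alone does not change the motor pattern. A statement of change, or of no change, needs a between-session yardstick.

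**Working it through.** **Step 1: the statements side by side.**

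| Place | What it commits to |
|---|---|
| Section A | a significance claim from any one participant |
| Section G, EMG collection paragraph | statistical testing, by reference to publications |
| Section G, co-activity and clonicity | valid inference on quantities and differences |
| Section j | no statistical analysis for comparing data |

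If section j governs, the first three have no analysis behind them. If any of the first three governs, section j is wrong.

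**Step 2: what the stated support covers.** The only figure is repeatability below 0.5%, from three repeats across five data sets. It is given without data and cannot be reproduced. The natural reading is re-analysis of the same data sets, although the text does not say so outright. It is not presented as a posterior SD or as a standard error. No source of between-session variation enters it, or enters the posterior as described.

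**Step 3: how much the omission could matter.** Let p be the posterior SD from one recording, s the session-to-session SD, and r = s/p. The document gives neither p nor s, so r is an assumed range. For one recording before and one after, using a normal approximation:

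- SE if only the posterior is counted: √2 · p
- true SE: √2 · √(p² + s²) = √2 · p · √(1 + r²)
- true coverage of a nominal 95% interval: 2Φ(1.96/√(1 + r²)) − 1

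For r = 1: √2 = 1.41, 1.96/1.41 = 1.39, coverage about 83%.

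| r (assumed) | SE understated by a factor of | True coverage |
|---|---|---|
| 0.25 | 1.03 | 94% |
| 0.5 | 1.12 | 92% |
| 1 | 1.41 | 83% |
| 2 | 2.24 | 62% |
| 5 | 5.10 | 30% |

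The effect runs from negligible to severe, and the document does not say where the study lies.

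**Step 4: where repeated recordings exist.** Stage 1C allows experiments to be repeated after surgery, with and without stimulation, over 10 to 14 days. Stage 2A allows weekly evaluation during post-surgery training. Both are optional. Stage 1A provides one set of measurements before the 80 screening sessions and a repeat at their end, with no replicate at either point. A participant's between-session spread may therefore be available after surgery, but not for the screening pair.

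**The case against.** The best defence has four parts.

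1. *Nothing in the protocol uses this method for a before-after inference.* The explicit before-after comparison is of mean and integrated EMG amplitude; co-activation is only to be calculated. This stands. A reader might infer that before-after changes will carry error bars that are far too small. The document does not support that: no section assigns the posterior or the 0.5% to a change over time, and under section j there would be no inferential error bars at all.
2. *The differences may be between muscles or parameters within one recording, where the posterior may be adequate.* This is possible. The sentence does not say so, which is the reason to limit it.
3. *The 0.5% is not offered as a standard error.* Correct. One could treat it as the whole error, giving a 95% half-width of 1.96 × √2 × 0.5% = 1.39% and, at assumed session SDs of 5%, 10% and 20%, coverage of 15%, 8% and 4%. Both inputs would come from outside the protocol, so these figures do not describe this plan.
4. *The study is a proof of principle without power, success is judged on standing and stepping against the historical best, and a separate analysis plan may exist.* This lowers the stakes for the EMG measures. It does not remove the contradiction, because section j excludes comparison rather than leaving it open, and the significance wording in section A concerns the success criterion itself.

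**Conclusion.** The contradiction is established on the face of the protocol: sections A and G promise what section j excludes. It is also established that a posterior for parameters of a signal and repeatability below 0.5% do not support inference on change in co-activity or clonicity between sessions.

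The size of the second problem is not established. It rests on the unknown ratio of session SD to posterior SD: about 94% coverage at one quarter, 83% at equality, lower if session variation dominates. The calculation assumes normality and a single recording at each time point.

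A reader might also infer that more recording sessions must be added. That does not follow for a study that claims no power and can restrict its statements. Nor would the optional weekly tests supply replicates around the screening training, because they fall after surgery.

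**What to change.** 1. **Section G, co-activity and clonicity:** limit the validity sentence to quantities and differences within one recording, and say that the posterior and the 0.5% do not include session-to-session variation.
2. **Section A:** replace the significance wording with a descriptive statement that the historical best was exceeded.
3. **Section G, EMG collection paragraph:** delete the general sentence on testing, or align it with section j.
4. **Section j:** state that results are descriptive for each participant. Show any before-after change beside that participant's between-session spread where weekly or repeated post-surgery recordings already exist. Make no inferential claim for the pair of measurements around the 80 screening sessions.

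The cost is editing and a little extra tabulation. The downside is weaker wording and less favourable statements of change. No extra sessions are required.
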